## **AIMS & HYPOTHESES FOR RANDOMIZED, WAITLIST-CONTROL STUDY.**

**Aim #1. To assess whether SafelyYou Guardian + HIL will lower fall rates.** Hypothesis 1. Compared to standard-of-care (waitlist control group), SafelyYou Guardian will reduce fall rates in study participant over the study period of 6 months.

**Aim #2. To assess how use of the SafelyYou Guardian affects time spent on the ground after a fall.** Longer time to fall discovery is associated with higher human suffering and often leads to higher medical morbidity/mortality. Hypothesis 2: SafelyYou Guardian + HIL will reduce time to fall discovery (time from fall to staff notification) to under 5 minutes and reduce time spent on the ground to under 15 minutes. Since there is no way to measure control participants time spend on the ground, the aim will not have a comparison but will be descriptive.

**Aim #3. To assess whether SafelyYou Guardian will lead to improvement in hard clinical outcomes.** Hypothesis 3: SafelyYou Guardian participants will lower ED visits and hospitalizations when compared to control. This reduction in ED and hospitalization will correlate with reduced fall rates (aim #1) and reduced time spent on the ground (aim #2). We will review the strength of the association with aim #1 and #2 outcomes.

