### Design

For Aim 1, we plan to recruit 460 study participants from 19 memory care facilities. For the purpose of this study, facilities will include Skilled Nursing Facilities (SNFs), or equivalent. Aim 1 will be a randomized controlled study using a waitlist control group. The randomization will occur at the individual (resident) level within each facility to control for variations at each facility in terms of facility size, facility administration, and staff training. During the first 6 months, n=230 will receive the intervention (SafelyYou Guardian, i.e. real-time alarms through a phone call from the HIL to the facility, front line staff intervention, and OT review), and n=230 will not receive the intervention. This design is the most rigorous way to test the intervention against the control: the randomization allows for control of confounding variables and has been previously used in the evaluation of medications, non-pharmacological, and mobile electronic interventions (where use of placebo treatment and blinding is not feasible) [87-89]. Previous work used a baseline as control, allowing possible confounding variables. As we recognize that 50% of the interested participants will not receive the intervention, those residents will be offered the intervention for a 6-month extension period (in order to accomplish Aim 2). This is the best compromise between the need for a rigorous randomized controlled trial vs. ethical responsibility to maximize benefit to each study participant.

For Aim #2, we will measure response times to each fall and the amount of time a resident spends on the ground after each fall. We intend to include all 460 participants' data from Aim #1. These will be participants who receive the initial intervention (n=230) and the additional participants who are on the waitlist control group who will receive the intervention in the second 6month period. The design for Aim #2 is observational in nature. The significance is that a large cohort of video data about the naturalistic progression of falls in residents with dementia has never been conducted to our knowledge. We will determine if the two time variables (time to fall discovery by staff and time spent on the ground after a fall, controlling

for baseline participant characteristics – i.e., demographics and medical conditions) and facility size, will predict need for ER visits or hospitalizations.

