#### Clinical outcomes.

For Aim #1, the primary outcomes are the number of falls detected by facilities using the adverse incident reporting system as per routine facility protocol. While use of video detected falls will be used in the intervention group to assist with prevention of future falls, we will not use this as the actual outcome measure: is not the standard-of-care, and the control group will not have video recorded outcomes. There is a bias for detecting falls using video since existing fall reporting systems do not capture falls which staff do not know about (e.g., when a resident is able to get back in bed after a fall). Staff-detected falls which automatically trigger adverse incident reporting is the “real-world” outcome measure and current stand-of-care. Thus, outcomes will differ by facility (each facility has different adverse incident reporting operations and implementation, hence the randomization at each facility will adjust for such variables).

Aim #2 will be a naturalistic observation of SafelyYou Guardian with HIL for 6 months. Specifically, for all the facilities, the use of the SafelyYou Guardian enables direct notification of falls to front-line staff in the facilities, by intervention of the HIL. We can directly measure time on the ground for the residents as follows: (1) The time of the fall is recorded by

SafelyYou Guardian (which detected it); (2) The time of intervention of the front-line staff is logged by the staff after finding the residents on the ground. This means that for the population with treatment, we can directly measure the time of fall discovery (successful call leading to front line staff intervention), and time on the ground (since time of the intervention is logged by the facility). This is because time on the ground for monitored residents can be measured precisely by video recording. Reduction of the time on the ground can be computed given the difference between the two.

Aim #3 will include number of ER visits and number of hospitalizations. We will obtain information about resident demographics, medical comorbidities, emergency room visits, and hospitalization data by asking the study participant legal representatives. In addition, we will have participant / participant Durable Power of Attorney complete HIPAA consent forms for release of medical records when indicated if the details of data are not available.

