Following the sample size for a time-averaged response methodology laid out in Fitzmaurice et al., we adjusted the total number of centers needed by a factor related to the number of observed months, anticipated participants per center (30% of 35 participants per center with 10% dropout) and the correlation between measurement months. The dropout rate was roughly at ~1% per month so a 10% dropout over 6 months is a conservative estimate. We assumed an extremely conservative estimate of the correlation between time points (months) of 0.8 and 6 months of follow-up. Reproducible R code is available at <https://github.com/[name]/>. We estimate that a total sample size of 460 ( $n=230/\text{arm}$ ) out of 19 facilities will be needed for a power of 80% to detect a 30% reduction in falls in the intervention group vs. control. Our approach of focusing on estimation and uncertainty and accepting the sample size collected for the main study, is congruent with experts' recommendations stating that the purpose of economic evaluation is not hypothesis testing; given there is no hypothesis testing, there is no requirement for a separate sample size calculation. For Aim 2, we will use similar descriptive statistics as described in Aim 1. For Aim 3, We will use a multivariate regression model to examine predictors of the main outcome, ER visits and hospitalizations (binary variable), using time to fall discovery by staff and time spent on the ground as the main predictors while controlling for baseline participant characteristics and facility characteristics.

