## **Risk/Benefit Assessment**

Minimal risk for study participants is expected as the system does not physically interact with study participants in any way and only provides supplementary support while all existing safety protocols in the facility remain in place.

Risks and/or discomforts include loss of privacy by placing a camera in the private room. Although the system is designed to keep video only when a fall is detected, false alarms do occur which can cause video to be uploaded at any time. If subjects feel uncomfortable about privacy once the cameras are installed, they may withdraw from the study at any time.

The research study personnel take several steps to protect the privacy of each participant. The recorded video does not have audio capability in order to protect private communication of residents and their visitors. Physical signs are posted visibly at the entrance to all private rooms containing cameras. The signs state that video recording is in progress to ensure all visitors and staff entering the room are aware of the camera. Cameras are placed in the private bedroom only, not in the private bathroom. Cameras record video only when an event is detected. Video (with no audio) will be reviewed by the research study personnel after collection. If more than one resident occupies a room, all roommates must provide informed consent for any to participate. All data is encrypted in transit and at rest.

Installation of the wall-mounted cameras will require inserting screws into the wall in the corner of the room adjacent to the ceiling and installing cabling which may be visible. No other risk of property damage is expected.

The ongoing safety procedures at the facility will remain in place.

The SafelyYou system has demonstrated reduced fall risk and unnecessary emergency room visits for those using it in previous studies with under 100 residents enrolled and hundreds more that have used it as a commercial product. We believe the system will provide significant benefits through faster response times to safety-critical situations, help staff make informed decisions about the need for transfer to the emergency room following unwitnessed falls, and reduce the overall frequency of falls through improved root cause analysis to minimize the risk of repeat falls, but this is active research, and we do not know if any of these benefits will occur for certain.

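### Aim 2 can time only the bedroom falls that the system detected, so its 5- and 15-minute results describe response given detection, not all falls of monitored residents

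*Combined protocol and SAP*

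**What the plan says.** The Design section states the scope of Aim 2 without restriction: "we will measure response times to each fall and the amount of time a resident spends on the ground after each fall".

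Hypothesis 2, under Aims & Hypotheses, sets two performance targets: to "reduce time to fall discovery (time from fall to staff notification) to under 5 minutes" and to "reduce time spent on the ground to under 15 minutes". It adds that "the aim will not have a comparison but will be descriptive", because control participants cannot be timed.

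Clinical outcomes then defines the measurement: "We can directly measure time on the ground for the residents as follows: (1) The time of the fall is recorded by", continuing "SafelyYou Guardian (which detected it); (2) The time of intervention of the front-line staff is logged by the staff after finding the residents". The same paragraph ties discovery to a call that succeeds and brings staff to the resident.

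Coverage is limited: "Cameras are placed in the private bedroom only, not in the private bathroom" (Risk/Benefit Assessment). The privacy section puts 5–10% of Phase I falls in bathrooms.

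The analysis text is one sentence: "For Aim 2, we will use similar descriptive statistics as described in Aim 1". The same Data analysis text makes the two times the main predictors of ER visits and hospitalizations in Aim 3.

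**The concern.** The stated scope is every fall, but the measurement exists only where the system registered the event. A fall that it missed triggers no call and has no start time. It therefore leaves the summary without trace, although it is a failure of the system under study.

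Calling the aim descriptive does not settle this. Hypothesis 2 claims that the system brings both times under fixed limits. With no comparator, the observed distribution is the only evidence for that claim, so the set of falls it covers decides what it means. A result restricted to detected falls answers how quickly help comes once the system has seen the fall. It does not answer how quickly monitored residents who fall are found. The same selection carries into the Aim 3 model.

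**Working it through.** The documents give no sample size, precision or detector sensitivity for Aim 2, so there is no planned figure to reproduce. The check has three parts.

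**1. Can a missed fall be timed by another route?**
- Video: the privacy section says that footage without a detected fall is discarded after 60 seconds. Event Detection describes a rolling 10-minute buffer, uploaded when an event is detected. The two statements should be reconciled, but under either one a missed fall that is found later cannot be timed from video.
- Incident reports: Data collection says that facilities file these for all known falls. They can show that a fall was missed, but they do not give the start time of an unwitnessed one.
- Nowhere does the plan match reports to alerts, estimate sensitivity or set a rule for untimed falls.

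**2. How many falls could be affected?**
Inputs: 460 participants and 6 months on the system (Design); 0.49 falls per resident-month and a 30% reduction (Data analysis). Attrition is ignored.
- Expected falls: 460 × 6 × 0.49 × 0.70 ≈ 947 (1,352 with no reduction).
- Untimed at an assumed miss rate of 5% or 10%: about 47 or 95.
- With 5–10% of falls in bathrooms as well, the timed share is (1 − bathroom share) × (1 − miss rate). It runs from 0.95 × 0.95 = 0.9025 to 0.90 × 0.90 = 0.81, leaving about 92 to 180 of 947 untimed (10% to 19%). Falls in common areas would add to this; the documents do not count them.

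**3. What does the selection do to the result?**
Let m be the share of falls missed, p the share of timed falls within target, and q the share of missed falls within target. The share for all falls is (1 − m)p + mq, so the timed-only result overstates it by

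p − [(1 − m)p + mq] = m(p − q).

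None of m, p and q is in the documents. With p = 90% assumed, the overstatement in percentage points is:

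| m | q = 0 | q = 50% | q = 95% |
|---|---|---|---|
| 1% | 0.9 | 0.4 | about 0 |
| 5% | 4.5 | 2.0 | −0.2 |
| 10% | 9.0 | 4.0 | −0.5 |
| 20% | 18.0 | 8.0 | −1.0 |

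Hypothesis 2 does not say whether its limits apply to a mean, a median or a share of falls. For a mean time on the ground, the all-falls value is (1 − m) × timed mean + m × missed mean. With a timed mean of 10 minutes (assumed), it reaches 15 minutes when m = 5 / (missed mean − 10):
- missed mean 120 minutes: m = 5/110 = 4.5%
- missed mean 60 minutes: m = 5/50 = 10%
- missed mean 30 minutes: m = 5/20 = 25%

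If missed falls average 5 minutes and m = 10%, the all-falls mean is 0.9 × 10 + 0.1 × 5 = 9.5 minutes, below the timed mean.

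**The case against.** A reader might infer that the missed falls are the long lies, so that both targets are flattered. The documents do not support this. They say nothing about how long undetected falls last. Event Detection triggers on a resident who is on the ground, so someone who stays down gives the system more chances, while a quick self-recovery is easily missed. A late detection still enters the data, and the buffer may help to place its start. For time on the ground, the sign of the bias is therefore open.

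A reader might also multiply an assumed success rate by sensitivity and take the product as the share for all falls. That sets q at zero. A fall that staff see in the room is discovered at once, even without an alert.

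Other points for the plan also stand. Slow verification, slow calls and slow staff response to an alert stay in the data; never-detected falls leave, and arguably those whose call did not succeed. The definition is open about its dependence on detection, and the aim is uncontrolled and descriptive.

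None of this supplies the missing denominator. For an unwitnessed fall that the system misses, no call is made and discovery waits on staff coming upon the resident. A favourable bias in discovery time is thus plausible for the falls the study is mainly about. The plan's own example of a fall unknown to staff, a resident who gets back into bed, produces no incident report. If the system also missed it, it would enter neither the timed falls nor the known falls.

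**Conclusion.** The point holds in a limited form. Aim 2 times will exist only for system-detected falls in camera-covered bedrooms, in conflict with the scope stated in Design, and nothing planned would show how many known falls are left out. The results describe response given detection.

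The bias is likely favourable for the 5-minute target when missed falls are unwitnessed, and of unknown sign for the 15-minute target. Over the assumed grid (p = 90%, m from 1% to 20%) it runs from 18 points of overstatement to 1 point of understatement. These figures are illustrations that rest on assumed values, not estimates for this system; the plan calls its detector highly accurate but gives no rate. The Aim 1 outcome, which uses facility-reported falls, is untouched. The Aim 3 time predictors inherit the selection.

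**What to change.** 1. For monitored residents, match incident reports to system alerts by resident and date. Use alerts confirmed as a resident on the ground, since the alert rule also fires when a resident sits up in bed.
2. Report timed falls over all known bedroom falls (from an alert or a report), and the matched detection rate.
3. Name the summary statistic for each target, and label the detected-only result as conditional on detection.
4. Add a worst-case bound that counts un-alerted, unwitnessed bedroom falls as missing both targets. List staff-witnessed falls separately; scoring them as failures would create a new bias.
5. List falls outside camera coverage, including bathrooms, separately, taking location from the incident report where recorded. Data collection does not name location as an item, so it may be incomplete.
6. State that the Aim 3 time predictors apply to detected falls only.

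Both data sources are already collected, so the cost is the matching work and some SAP text. The headline figures may become less favourable. Missed falls that staff never learn of stay uncounted, and an alert itself makes a report more likely, so the matched detection rate should be read as an upper guide to true sensitivity.

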#### **Data collection:**

Demographic and clinical data set: We collect demographic data including age, gender, race/ethnicity, primary clinical diagnoses for SNF stay with specific focus on dementia subtype, most recent orthopedic surgery (<3 months) or reason for hospitalization, chronic medical conditions (top 3), and baseline medications (number of medications). Beyond the data collected from the video, data specific to the falls is collected either by direct extraction from the platform or from incident reports kept by facilities as (State regulations require facility track and file incident reports for all known falls). For the control population, the time of unwitnessed falls is unknown, but the number of falls and ER visits is collected from the existing facility incident reports. For the population equipped with SafelyYou Guardian, we will have direct access to the time of the fall, the time it took the HIL to verify the fall and call the facility, and the time on the ground. Note that for the residents with SafelyYou Guardian, we expect these values to be in increments of minutes.

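### The numbered rule for time on the ground stops the clock at a staff-logged intervention, a later sentence relies on video, and the plan does not say which prevails or make leaving the floor the end event

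*Combined protocol and SAP*

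**What the plan says.** All references are to the combined protocol and SAP.

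- **Targets (Aims & Hypotheses, Aim #2).** Hypothesis 2 is that the system will "reduce time to fall discovery (time from fall to staff notification) to under 5 minutes". Its second target, for the floor interval, is to "reduce time spent on the ground to under 15 minutes". Discovery has an end point in this section; time on the ground has none. Controls cannot be timed, so "the aim will not have a comparison but will be descriptive".
- **Numbered rule (Clinical outcomes).** Item 1 is the fall time recorded by the system. Item 2 is "The time of intervention of the front-line staff is logged by the staff after finding the residents on the ground". The next sentence gives the facility's logging of the intervention as the reason why time on the ground is measurable.
- **Video (Clinical outcomes, same paragraph).** The text then says "time on the ground for monitored residents can be measured precisely by video recording". It ends by saying that the reduction is the difference between two quantities, which it does not identify.
- **Discovery (Clinical outcomes).** Here the wording is "the time of fall discovery (successful call leading to front line staff intervention", against "time from fall to staff notification" under Aim #2.
- **Data items (Data collection).** For monitored residents the plan lists the fall time, "the time it took the HIL to verify the fall and call the facility, and the time on the ground". Time on the ground is thus a separate item, with no end event given.
- **Later use (Data analysis).** Aim 2 is summarised descriptively. Both times are the main predictors in the Aim 3 regression for ER visits and hospitalizations.

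**The concern.** An interval that starts at the fall and ends when staff intervene measures how fast staff respond. A resident who is assessed and helped up after that moment is still on the ground, and the numbered rule does not count those minutes. The plan gives a second basis, video, which could count them, but does not connect the two.

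Aim 2 has no comparator, so the result is simply the measured times set against 5 and 15 minutes. The choice of end event therefore bears directly on what is reported, and two analysts could follow different sentences of the same paragraph and report different attainment.

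The 5-minute target raises a smaller question. If discovery needs a call that actually brings staff to the resident, a fall whose call brought no response has no discovery time. The slowest cases could then leave the summary unnoticed.

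**Working it through.** The plan derives no figure on this point: both targets are stated, not calculated. The check compares definitions and then illustrates how much the end event can matter.

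**Step 1. Time on the ground.**

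| Place | Start | End | Source |
|---|---|---|---|
| Aim #2 | not stated | not stated | not stated |
| Data collection | fall time (listed as its own item) | not stated | direct access for monitored residents |
| Clinical outcomes, numbered rule | system fall time | staff intervention | facility log |
| Clinical outcomes, later sentence | not stated | not stated | video |

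Only the numbered rule names both ends, and its end is intervention. No row ends at the resident leaving the floor, and no sentence ranks log against video.

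**Step 2. Direction.** Let R be the time from fall to logged intervention, and L the further time on the floor. True time on the ground is R + L, and the rule records R. With L ≥ 0, P(R < 15) ≥ P(R + L < 15), so the rule can only flatter the target for residents who are still down when the intervention is logged.

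**Step 3. Illustration A.** The documents give no distribution for R or L. Assume R is exponential with mean m, and L is fixed. Then P(R < 15) = 1 − exp(−15/m) and P(R + L < 15) = 1 − exp(−(15 − L)/m).

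| m (min) | clock stops at intervention | L = 2 min | L = 5 min | L = 10 min |
|---|---|---|---|---|
| 3 | 99.3% | 98.7% | 96.4% | 81.1% |
| 5 | 95.0% | 92.6% | 86.5% | 63.2% |
| 8 | 84.7% | 80.3% | 71.3% | 46.5% |

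The smallest loss is 99.3 − 98.7 = 0.6 points, about 1. The largest is 84.7 − 46.5 = 38.2 points.

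**Step 4. Illustration B.** Assume R is lognormal with median 6 minutes and log SD 0.7. Then P(R < t) = Φ(ln(t/6)/0.7).

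- Clock stops at intervention: Φ(ln(15/6)/0.7) = Φ(1.31) = 90.5%.
- L = 3: Φ(ln(12/6)/0.7) = Φ(0.99) = 83.9%, a loss of 6.6 points.
- L = 5: Φ(ln(10/6)/0.7) = Φ(0.73) = 76.7%, a loss of 13.8 points.
- L = 10: Φ(ln(5/6)/0.7) = Φ(−0.26) = 39.7%, a loss of 50.8 points.

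**Step 5. Discovery.** Suppose n falls are detected, k of them have a call that brings no response, and s are discovered in under 5 minutes. If discovery requires staff intervention and the k falls are left out, the reported share is s/(n − k). If they are kept as not meeting the target, it is s/n. The first is larger whenever k and s are above zero. The documents give no value for k.

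**The case against.** The strongest reply is that the plan already has a video basis. Clinical outcomes says so, Data collection lists time on the ground as its own item, and the Event Detection paragraph says upload continues while a resident is detected on the ground. In ordinary language, time on the ground lasts until the person is off it. The phrase about logging after finding the resident may also describe only when the entry is made. This stands to the extent that the plan cannot be said to have settled on time of finding. It does not remove the problem: the event logged is still intervention, the video sentence states a capability without an end event, and the only complete rule is the staff-log one.

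On discovery, notification and a successful call may be the same event, since the call is how staff are notified. That is a fair reading. The Data collection item on verifying and calling is never labelled discovery, so it should not be counted as a further definition. What remains is that the Clinical outcomes wording can also be read as requiring a staff response.

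Aim 2 is descriptive and has no test. Hypothesis 2 does not say whether its limits apply to a mean, a median or a share of falls, so the percentages above rest on a criterion chosen for illustration, as well as on assumed distributions. This also stands.

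A reader might infer that the Aim 3 regression is biased. The documents do not show it. A constant extra delay only shifts a predictor that is entered linearly and leaves its slope unchanged; bias would need a delay that varies with severity or outcome. What can be said is conditional: if both times end at staff intervention, they become nearly the same variable and their separate associations would be hard to estimate.

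**Conclusion.** The point holds as a defect of definition with a known direction. The numbered rule yields a response time, the same paragraph points to video, and nothing reconciles the two. If the rule is followed as written, attainment of the 15-minute target will look better than it is. This assumes that residents are still on the floor when the intervention is logged and that the logged time precedes their leaving it.

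The size cannot be derived from the documents. The assumed cases mostly give a loss of about 1 to 38 percentage points, and the most extreme gives 51. They show that the end event can matter, and none predicts the trial's value.

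For discovery, the two wordings should be made one. Loss of unanswered calls from the 5-minute summary is a risk under one reading, not an established fault.

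A reader might conclude that both targets will be judged on the wrong intervals. The text does not support that: the video route is open, and the discovery wordings may agree. This should be corrected before analysis. It does not touch the randomised comparison in Aim 1.

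**What to change.** Reconcile Aim #2, Data collection, Clinical outcomes and the Aim 3 part of Data analysis with one definition for each time.

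- **Time on the ground:** from the video time at which the resident reaches the floor to the video time at which the resident is off it. Use the staff log only when video is unavailable, flag those falls, and report how many there are.
- **Time to discovery:** from the same start to the logged notification of staff, by phone or e-call as the Event Detection paragraph allows. Keep falls without a successful notification in the denominator and count them as not meeting the 5-minute target.
- **Aim 3:** use these same two definitions for the predictors.
- **Reduction:** state which two quantities are differenced, or delete the sentence.

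The cost is revised wording, plus reading video time stamps for each fall. The footage is already uploaded while the resident is detected on the ground, and the Risk/Benefit Assessment says study personnel review it. Notification times must be logged consistently for both contact routes. The visible downside is that times on the ground will look longer than under the staff-log rule. Recruitment, randomisation and sample size do not change.

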For aim #3, we will ascertain the occurrence of fall in the intervention group by doing follow-up case review of each detected fall. For the control group, we perform biweekly check with facility staff and family regarding knowledge and documentation of any falls. For falls in both the intervention and control group, we will additional collected data regarding occurrence of ED visit and hospitalization days. We will also include occurrence (or absence) of any operations, intensive care unit stays, and other medical procedures. We will also collect mortality data.

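### Aim 3 is tied to falls in some sections and unrestricted in others, with different sources and scales, so two analysts could count different ED visits and hospitalizations

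*Combined protocol and SAP*

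**What the plan says.** Five places in the combined protocol and SAP bear on what counts for Aim 3.

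- **Aims & Hypotheses, Hypothesis 3:** "SafelyYou Guardian participants will lower ED visits and hospitalizations when compared to control". No cause of visit is attached.
- **Design, Aim 3 paragraph:** "For falls in both the intervention and control group, we will additional collected data regarding occurrence of ED visit and hospitalization days". Collection starts from a fall. The same paragraph finds falls by case review of each detected fall in the intervention arm, and by biweekly checks with staff and family in the control arm.
- **Data collection:** for controls, "the number of falls and ER visits is collected from the existing facility incident reports". The section describes these reports as the ones facilities must file for falls they know of.
- **Clinical outcomes, Aim 3 paragraph:** "Aim #3 will include number of ER visits and number of hospitalizations". The plan obtains "emergency room visits, and hospitalization data by asking the study participant legal representatives", with released medical records where details are missing. No link to a fall is stated.
- **Clinical outcomes, data analysis paragraph:** the regression examines "predictors of the main outcome, ER visits and hospitalizations (binary variable), using time to fall discovery by staff" and time on the ground. The outcome is binary and its cause is not stated.

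No section says which of these governs Hypothesis 3.

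**The concern.** An ED visit for an infection counts under Hypothesis 3 and the Clinical outcomes section as written. Under the Design section it is never collected. The intervention is meant to act through falls and the response to them, so the unrestricted set is likely to include visits it cannot change, while the fall-linked set depends on someone attributing the visit to a fall.

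Three things are at stake.

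- **Interpretation.** A null result on unrestricted visits could be read as no clinical benefit when it partly reflects dilution.
- **Comparability of the arms.** If only visits attached to a known fall are recorded, the chance of recording a visit depends on how falls are found, and that differs by arm. For Aim 1 the plan recognises this problem and declines to use video-detected falls as the outcome. It states no such safeguard for Aim 3.
- **Timing of the choice.** The Design section says blinding is not feasible. An open definition leaves room to settle it after results are known, and visits that were never recorded cannot be recovered later.

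**Working it through.** **Step 1. The sections side by side.**

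| Section | Which events | Source | Scale |
|---|---|---|---|
| Aims & Hypotheses | No restriction | Not stated | Not stated |
| Design | Attached to a fall | Detected-fall case review (intervention); biweekly checks (control) | Occurrence of ED visit; hospitalization days |
| Data collection | ER visits, controls only | Incident reports for known falls | Number |
| Clinical outcomes, Aim 3 | No restriction | Legal representatives, records if needed | Number |
| Clinical outcomes, data analysis | Not stated | Not stated | Binary |

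The set of events, the source and the scale each take more than one value. The source for control-arm ER visits is given in two incompatible ways, and only the incident-report version is specific to one arm.

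**Step 2. Is there a plan figure to reproduce?** Not for Aim 3. The only sample size ("We estimate that a total sample size of 460") is set for "a power of 80% to detect a 30% reduction in falls in the intervention group vs. control". No ED or hospitalization rate, fall share of visits or Aim 3 power appears anywhere. Everything below is therefore illustration.

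**Step 3. Dilution.** Let *f* be the share of control-arm visits caused by falls. Suppose treatment cuts fall-related visits by 37% and leaves the others unchanged. The 37% is the pilots' reduction in EMS use for falls (Privacy and security safeguards), borrowed here for ED visits. Then RR = 1 − 0.37*f*:

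- *f* = 1: 1 − 0.37 = 0.63
- *f* = 0.5: 1 − 0.185 = 0.815
- *f* = 0.3: 1 − 0.111 = 0.889

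**Step 4. What this could do to a comparison of counts.** Assume a two-sided 5% Wald test on the log rate ratio, 230 per arm, and 0.6 fall-related visits per control resident over 6 months. That is about 20% of the 0.49 × 6 = 2.94 falls implied by the pilot rate. With m₀ = 0.6/*f* and between-resident variance k:

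Var(log RR) = 1/(230 m₀) + 1/(230 m₀ RR) + 2k/230

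For *f* = 1, k = 0: variance = 1/138 + 1/(138 × 0.63) = 0.01875, SE = 0.137, |log RR|/SE = 0.462/0.137 = 3.37, power 92%. For *f* = 0.3, k = 0: m₀ = 2, variance = 1/460 + 1/(460 × 0.889) = 0.00462, SE = 0.068, ratio 1.73, power 41%.

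| *f* | RR | Power, k = 0 | Power, k = 1 |
|---|---|---|---|
| 1 | 0.63 | 92% | 80% |
| 0.5 | 0.815 | 62% | 35% |
| 0.3 | 0.889 | 41% | 17% |

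**Step 5. A second set of assumptions.** Simulation with 20,000 trials per scenario and 207 per arm (230 less the plan's 10% dropout). Assumed: 5–20% of falls lead to an ED visit (0.05 × 2.94 = 0.15 to 0.20 × 2.94 = 0.59 per control resident), 0.1–1.0 other visits per resident unaffected by treatment, dispersion 0 or 1.

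- A 30% cut in fall-related visits becomes a 4–26% cut in all visits; a 37% cut becomes 5–32%. Example: 0.37 × 0.588/(0.588 + 1.0) = 14%.
- Power was 21–89% on fall-related visits and 5–83% on all visits.
- The same trial was significant on fall-related visits but not on all visits in 8–49% of runs. The reverse occurred in 1–5%.

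Neither calculation models facility clustering or treats hospitalizations separately.

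**The case against.** The strongest reply is that this is silence set against a restriction. No section uses the term all-cause. The Clinical outcomes entry is a short list and Hypothesis 3 is one line, while the Design paragraph is the specific collection text for Aim 3 and can be read as governing. The expected correlation with fall rate and time on the ground, the predictors in the Aim 3 regression, and the benefit claimed in the Risk/Benefit Assessment for transfers after unwitnessed falls all point the same way. This stands far enough to rule out saying that the plan defines an all-cause outcome. It does not settle the matter: the section that defines outcomes asks representatives about visits generally and gives no attribution rule, and nothing says that the Design paragraph takes precedence.

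A reader might also infer that Hypothesis 3 would pass under one definition and fail under the other. The documents do not support that. The only Aim 3 model uses time to discovery and time on the ground, and the Aims section says time on the ground cannot be measured in controls. No between-arm test is specified, so the test in Steps 4 and 5 is an assumption, as are the visit rates. The 37% concerns EMS use in pilots that, according to the Design section, used a baseline as control.

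Nor do the documents show that the fall-related count should lead. Attribution would rest partly on unblinded informants, and the Purpose section says video can show that a resident moved to the ground intentionally. The same event could therefore be labelled a fall in one arm and not in the other. An unrestricted count avoids that judgement.

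Finally, the Clinical outcomes section assigns the primary outcomes to Aim 1, which limits how serious this can be.

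**Conclusion.** The inconsistency is real and should be repaired. Aim 3 is fall-linked in the Design section and, for control-arm ER visits, in the Data collection section. It is unrestricted in Hypothesis 3 and the Clinical outcomes section. The scale differs as well. Two analysts could count different events, and under the fall-linked text the capture of events depends on fall-finding methods that differ by arm. The direction of that effect cannot be determined from the documents.

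The textual conflict needs no assumption. Its numerical size does: the rate ratio of 0.63 to 0.89 holds if the pilot's 37% carries over to fall-related visits, other visits are unaffected, and falls cause 100% to 30% of visits. The power figures show the direction of the dilution and are not estimates for this trial. Because Aim 3 is not the primary outcome, this is a change the sponsor should make; it does not undermine the trial's main comparison.

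**What to change.** Reconcile Aims & Hypotheses, Design, Data collection, and both the Aim 3 and data analysis paragraphs under Clinical outcomes, as follows.

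1. Record every ED visit and hospitalization in both arms over the 6-month randomized period, whether or not a fall was detected or reported. Use the same source in each arm: the legal representative, with released records where needed, as the Clinical outcomes section already plans.
2. Code each event as fall-related or not by one written rule applied identically in both arms, blind to arm where the record allows.
3. Before any outcome data are seen, name one definition and one scale for the Hypothesis 3 between-arm comparison, and report the other definition beside it. Which one leads is the sponsor's choice.

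The cost is protocol and analysis wording plus one coded field per event. A limitation remains: the fall-related count is open to attribution bias because informants are unblinded. The unrestricted count reported beside it helps to check this.
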